### 9. Analysis Plan

#### a. Methods

A note on the choice of analysis methods: For analysis results to have a tenable interpretation, it is important that the analysis methods be appropriate for the target causal parameters of interest. Thus, when comparing estimates from a collection of specific statistical methods, care is needed to ensure that all the methods under consideration can be used to estimate the same causal parameter (and that they can do so under compatible causal assumptions). Consider two concrete examples of direct relevance to this proposal: (1): single equation, multivariable single equation regression methods (i.e., maximum likelihood estimation of the coefficients of a multi-variable regression) estimate conditional average treatment effects (conditional on all the covariates entered in the regression together with the treatment indicators). For non-linear regression models (including the popular logistic regression and Cox proportional hazards regression models) these conditional average treatment effects are not in general equal to the corresponding population-averaged (marginal) causal effects. For instance, the coefficient from a multivariable logistic regression model of the outcome on treatment and covariates does not equal to the marginal odds ratio, even if the multivariable regression model is correctly specified and in the absence of any unmeasured confounding (this phenomenon relates to the non-collapsibility of the odds ratio; in general the conditional odds ratio is expected to be further away from the null compared to the marginal odds ratio, except in rare cases). (2) Inverse probability weighting, matching, and instrumental variable estimators do not estimate the same population-averaged causal effects: Specifically, *inverse probability weighing* targets the average treatment effect in the entire population (or the average treatment effect in the treated/controls, with appropriate choice of odds weights). Matching methods estimate causal effects in populations that depend on the data generating mechanism and the matching algorithm (e.g., 1-to-1 matching without replacement, when one treatment is much less commonly prescribed than the comparator produces estimates of the average treatment effect in the population treated with the rarely prescribed treatment). Lastly, instrumental variable methods estimate different causal parameters depending on auxiliary assumptions that are untestable; under homogeneity, they estimate the average treatment effect; under certain structural nested mean models

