Intention-to-treat effect in the treated (unadjusted for non-adherence)	Marginal difference of survival probabilities as specified time points & survival curves for each treatment	
 
(8) Matching on the estimated probability of treatment, followed by non-parametric modeling of the survival probability as a function of time, in each treatment group
 
(9) Marginal structural survival probability model with time-varying marginal counterfactual hazards (in the total study sample); inverse odds of treatment weighting
 
(10) Matching followed by Cox propertional bazards
 
	Using indicator functions for time-periods and interactions with treatment group this approach avoids proportional hazards assumptions. Naïve nonparametric bootstrap inference is not appropriate for some matching estimators because they are non-smooth (see the text of the proposal for how we intend to address this).				
	iviarginal nazaro ratio	(10) matching followed by Cox proportional nazards	Same as above.				

	(averaged over the follow-up period)	regression (11) Marginal structural Cox proportional hazards model; inverse probability of treatment weighting					
Per-protocol effects (i.e., adjusted for non- adherence)	Marginal difference of survival probabilities as specified time points	
 
(12) g-formula computation; outcome model-based standardization following nested regression
 
(13) Marginal structural model with time-varying hazard; inverse probability of treatment weighting
 
(14) g-estimation of accelerated failure time model
 
	These methods can account for observed non-adherence and estimate the effects of complete adherence or partial adherence.				
LEAD-2 trial (continuous outcome evaluated at the end of the study)							
Intention-to-treat conditional treatment effect	Conditional mean difference ratio	(15) Multivariable conditional outcome model; adjusted ordinary least squares regression	These approaches correspond to the "single equation method" asked for in the RFP. Note that marginalizing over the baseline covariates is equivalent to approach (13) below.				

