Intention-to-treat effect in the total population of eligible individuals (i.e., unadjusted for non-adherence)	Marginal mean difference at the end of the study	
 
(16) g-formula computation; outcome model-based standardization following outcome regression
 
(17) Marginal structural mean model; inverse probability of treatment weighting
 
(18) Efficient and doubly robust estimation using estimating equations
 
(19) Efficient and doubly robust estimation using TMLE
 
(20) Nested structural mean model; g-estimation
 
	Approach (16) also addresses early dropout from the study. Approach (17) needs to be combined with inverse probability of outcome missingness (i.e., no early drop-out) to account for individuals who do not have measurements at the end of the study. Inverse probability of outcome missingness weights can also be used with approaches (18) through (20).				
Intention-to-treat effect in the treated (i.e., unadjusted for non-adherence)	Marginal mean difference at the end of the study	
 
(21) Matching on the estimated probability of treatment
 
(i.e., the propensity score)
 
(22) Marginal structural mean model (in the total study sample); inverse odds of treatment weighting
 
	Using indicator functions for time-periods and interactions with treatment group this approach avoids proportional hazards assumptions. Naïve nonparametric bootstrap inference is not appropriate for some matching estimators because they are non-smooth (see the text of the proposal for how we intend to address this).				
Per-protocol effects (i.e., adjusted for non- adherence)	Marginal mean difference at the end of the study	
 
(23) g-formula computation; outcome model-based standardization following nested regression
 
(24) Marginal structural mean model for time-varying treatments; inverse probability of treatment weighting
 
(25) Nested structural mean model for time-varying treatments; g-estimation
 
	These methods can account for observed non-adherence and estimate the effects of complete adherence or partial adherence.				

RFP = request for proposals; TMLE = targeted minimum loss estimation.

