**Dealing with extreme weights in weighted analyses:** Many of the estimation approaches we propose to use involve the estimation of inverse probability weights (for treatment initiation, censoring, or non-adherence). These estimation approaches are sensitive to near-violations and violations of related positivity assumptions (i.e., the assumptions of positive probability of treatment assignment, of no-censoring, and of full adherence). We will address issues related to extreme weights using an explicit bias-variance tradeoff framework. After estimating the weights, and before estimating treatment effects, we will begin by finetuning our selection criteria and examining the covariates that may be responsible for the extreme weights. If difficulties persist, we will repeat our analyses after trimming or truncating extreme weights using from the 99th to the 95th percentile of the weight distribution to define "extreme" weights.

**Matching estimators:** We have noted above the difficulties when comparing the results from matching estimators against other methods of estimation for population-averaged causal effects (e.g., IP weighting). In the table, we have listed matching as estimating the average treatment effect on the treated because our background knowledge and the preliminary counts reported in **Section 11b** suggest that the treatment group corresponding to the "experimental intervention" in the emulated trial will be less common than the treatment group corresponding to the "control intervention"; in such cases, matching methods (unless combined with additional weighting) approximately estimate the average treatment effect in the population of patients treated with the experimental intervention (i.e., the average treatment effect on the treated). We will use 1-to-many matching on the propensity score with replacement, within calipers of 0.1 standard deviation (on the logit-propensity score scale). Because matching estimators are non-smooth we will consider to use of the m-out-of-n bootstrap and the methods described by Otsu et al. to improve the performance of bootstrap methods ([name] is currently supervising a PhD student, not budget for in this proposal, who has already implemented methods to address these very issues).

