### Comparisons between the observational analysis results and the target trial, and

**comparisons among different estimators:** We will use the bootstrap results described above to compare treatment effect estimates from the observational analyses against the published randomized trial results. As suggested in the RFP, we will use the following criteria to organize our comparisons: (1) regulatory agreement, defined as statistically significant result with directional equivalence between the RCT and observational study; and (2) estimate agreement, defined as the point estimate of the observational study falling within the 95% confidence interval of the ATE from the RCT using the reported standard errors of the RCT to define the confidence interval. We also believe that the following additional comparison may be useful: (3) estimate the point estimate and confidence interval for the ratio or difference of the trial estimate vs. the corresponding observational study estimate (the choice between taking the difference of the estimators or their ratio will be based on whether the effect measure is additive or multiplicative, respectively).

Last, we will use the bootstrap results to compare the treatment effect estimators listed in **Table 3** when appropriate, that is, when the estimators share the same target parameter

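### The 0.1 SD matching caliper can leave treated patients unmatched; (8), (10) and (21) then estimate the effect in the matched treated, yet Table 3 gives them the same target as odds weighting.

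*Protocol*

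**What the plan says.** Four statements in Section 9a (Methods) bear on this.

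- **Algorithm.** The paragraph on matching estimators fixes the design: "We will use 1-to-many matching on the propensity score with replacement, within calipers of 0.1 standard deviation", measured on the logit of the propensity score.
- **Target claimed.** The same paragraph expects the experimental drug to be the rarer one. It says that in such cases matching methods, unless combined with further weighting, "approximately estimate the average treatment effect in the population of patients treated with the experimental intervention".
- **Shared rows.** For ROCKET, the Table 3 block on the intention-to-treat effect in the treated holds matching (8) and odds weighting (9) for survival differences, and matching (10) and a weighted Cox model (11) for hazard ratios. For LEAD-2, the corresponding block holds matching (21) and odds weighting (22). Approaches (9) and (22) are specified in the total study sample.
- **Comparison rule.** The closing paragraph on comparisons allows estimators to be set against each other when appropriate, "that is, when the estimators share the same target parameter".

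The opening note of Section 9a adds a general caution: "Matching methods estimate causal effects in populations that depend on the data generating mechanism and the matching algorithm". Its example is 1-to-1 matching without replacement. Nothing in the document says that a caliper can exclude treated patients, or that the target then changes.

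**The concern.** A caliper can remove treated patients, typically those whose propensity score is so high that no comparator lies close by. Odds weighting in the total sample keeps them in the target population. Once anyone is removed, the two approaches describe different patients although Table 3 gives them one label.

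Rarity does not settle this. Under 1-to-1 matching without replacement, a rare treatment tends to make the matched population the treated population. Here comparators are reused, so they cannot run out. What can exclude treated patients is the caliper together with the overlap of the scores.

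Comparing methods and data samples is a stated objective (Section 1c, items 4 and 5). A gap between (8) and (9), or (21) and (22), could be read as a difference between methods when part of it is a difference between patients. The share dropped depends on cohort size and score separation, and both can change across the three cohorts. Section 1c itself says that EHR linkage will substantially reduce the sample and add covariates. The matched target could therefore drift between cohorts as well.

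**Working it through.** The protocol states no matched fraction, so there is no figure to reproduce. The check shows when the targets part and by how much under stated assumptions.

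**1. Identity.** Let p be the share of treated patients dropped, K the mean effect in those kept and D the mean effect in those dropped. The effect in all the treated is ATT = (1 − p)K + pD. Hence

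K − ATT = p(K − D).

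The gap is zero if nobody is dropped (p = 0) or if kept and dropped patients have the same mean effect (K = D). Both conditions must fail for the comparison to be distorted.

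**2. Inputs from the protocol.** Caliper 0.1 SD on the logit score, with replacement (Section 9a). Preliminary counts since approval (Section 9b): 19,710 with a rivaroxaban claim and 48,380 with a warfarin claim, so 48,380 / 19,710 = 2.45 comparators per treated patient. Section 9b expects a substantial reduction after eligibility but gives no amount. It gives no EHR-linked counts and no LEAD-2 comparator count.

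**3. Assumptions.** Logit score N(0, 1) in comparators and N(d, 1) or N(d, 1.5²) in the treated. The caliper is 0.1 times the SD of the score over all patients. A treated patient is dropped if no comparator lies within it. Arm sizes are 100%, 10% and 1% of the ROCKET counts. With equal SDs, AUC = Φ(d/√2), so d = 1.0 corresponds to 0.76 and d = 2.0 to 0.92.

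**4. Share of treated dropped (simulation).**

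| Separation d, treated SD | 19,710 v 48,380 | 1,971 v 4,838 | 197 v 484 |
|---|---|---|---|
| 0.25, SD 1 | 0.01% | 0.07% | 1.1% |
| 1.0, SD 1 | 0.1% | 0.6% | 3.7% |
| 2.0, SD 1 | 1.0% | 5.5% | 19% |
| 3.0, SD 1 | 9.3% | 26% | 46% |
| 0.5, SD 1.5 | 0.8% | 2.5% | 6.3% |
| 1.0, SD 1.5 | 1.9% | 5.2% | 11% |
| 2.0, SD 1.5 | 5.6% | 15% | 29% |

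These figures carry simulation error in the last digit. A separate simulation with 2,000 treated and 5,000 comparators at d = 2.0 gave 5%, in line with the 5.5% above.

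**5. Effect on the estimand.** Assume each treated patient's effect is 1 + 0.5 × (score − d)/SD, so the true ATT is 1.0. With SD 1, the mean effect in the matched treated is:

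| d | 19,710 v 48,380 | 1,971 v 4,838 | 197 v 484 |
|---|---|---|---|
| 1.0 | 1.00 | 0.99 | 0.94 (simulated ATT 0.98) |
| 2.0 | 0.99 | 0.94 | 0.85 |
| 3.0 | 0.91 | 0.79 | 0.68 |

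**6. Check against the identity.** At d = 2.0 with 197 v 484, p = 0.1855, K = 0.845 and the simulated ATT is 1.001. So K − D = (0.845 − 1.001)/0.1855 = −0.84. The dropped patients have a mean effect of about 1.69, as expected if the effect rises with the score and the highest scores are lost.

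**The case against.** A reader might infer that the caliper does drop patients here, and so that (8), (10) and (21) do not estimate the effect in the treated. The documents do not support that. They report no overlap, matching is with replacement, and at the only arm counts given the loss is about 1% or less unless separation is very large or the treated scores are more spread out. Large losses appear only under assumed shrinkage or poor overlap. This objection stands, and the point is conditional.

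The protocol also hedges. It says that matching targets depend on the algorithm, that comparing matching with other methods is difficult, that matching gives the effect in the treated only approximately, and that comparisons are made when appropriate. This stands in part. The approximation is tied to rarity, and the general caution is not carried through to the plan's own caliper or to Table 3.

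Nor is odds weighting a fixed benchmark. Where treated patients lack close comparators, those comparators carry extreme weights. Section 9a then allows selection criteria to be adjusted and weights to be trimmed or truncated, and either can change what (9) and (22) estimate. This stands, and the fix takes it in.

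It would also be wrong to set (10) against (9): one is a hazard ratio, the other a survival difference. The counterpart of (10) is (11).

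Finally, reporting how many patients were unmatched is ordinary analysis-plan detail, which Section 9a defers. Its absence is not the point made here. The caliper, the label, its rationale and the comparison rule are all fixed in this document, and they do not fit together once anyone is unmatched.

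**Conclusion.** The point holds as a conditional one of minor weight. Whenever the caliper leaves treated patients unmatched, (8), (10) and (21) estimate the effect in the matched treated. Table 3 and the comparison rule would still treat (8) and (9), and (21) and (22), as sharing a target.

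Under the assumptions above the consequence is negligible in a large claims cohort with good overlap. It can become material in much smaller cohorts or with poor overlap. The EHR-linked cohorts and LEAD-2 are where this most needs checking, but the documents give no counts from which to say that it will occur there. The simulated figures are a range, not a prediction for these data, and the estimand shifts also rest on an assumed effect gradient.

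**What to change.** - When any treated patient is unmatched, label the target of (8), (10) and (21) in Table 3 as the effect in the matched treated.
- For method comparisons, also run (9) and (22) with the treated limited to those retained by matching, and compare (8) and (21) with these.
- For (10), run an odds-weighted version of (11) on the same restricted treated group. Table 3 describes (11) as inverse probability of treatment weighting, and Section 9a says that odds weights are what target the treated.
- Keep the full-treated weighted analyses as the estimate of the effect in the treated, and note any trimming of weights or change of selection criteria that alters their population.

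**Cost.** A wording change and a rerun of existing weighting code. The retained set depends on the estimated score, so the restricted runs must be repeated for each cohort and nested in the bootstrap, and in the imputation for the stability analysis. That is modest extra computing.

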### Comparisons between the observational analysis results and the target trial, and

**comparisons among different estimators:** We will use the bootstrap results described above to compare treatment effect estimates from the observational analyses against the published randomized trial results. As suggested in the RFP, we will use the following criteria to organize our comparisons: (1) regulatory agreement, defined as statistically significant result with directional equivalence between the RCT and observational study; and (2) estimate agreement, defined as the point estimate of the observational study falling within the 95% confidence interval of the ATE from the RCT using the reported standard errors of the RCT to define the confidence interval. We also believe that the following additional comparison may be useful: (3) estimate the point estimate and confidence interval for the ratio or difference of the trial estimate vs. the corresponding observational study estimate (the choice between taking the difference of the estimators or their ratio will be based on whether the effect measure is additive or multiplicative, respectively).

Last, we will use the bootstrap results to compare the treatment effect estimators listed in **Table 3** when appropriate, that is, when the estimators share the same target parameter

### b. Preliminary Patient Counts

Counts were obtained using OptumLab's Natural History of Disease tool using data current as of Jan 16, 2018.

	Data years	
Торіс	1994 - 2018	From drug approval for indication - 2018
ROCKET trial emulation		
Individuals with atrial fibrillation claims	270,461	153,637
Individuals with at least one claim for warfarin treatment	102,089	48,380
Individuals with at least one claim for rivaroxaban	23,230	19,710
LEAD-2 trial emulation		
Individuals with diabetes claims	746,221	359,587
Individuals with diabetes and liraglutide claims	11,804	5,840
Individuals with diabetes and liraglutide + metformin claims (estimated value due to limitations of the NHB tool)	10,671	5,054

NHD = Natural History of Disease.

Although we expect substantial reduction in sample size as we apply the additional selection criteria listed in Tables 1 and 2, the above preliminary counts suggest that we will have adequate sample size to precisely estimate the target parameters of interest. Note that **we have** 

*decided not to perform any power calculations* for this proposal because of the undue influence they place on statistical significance (which is particularly inappropriate in observational studies) and because their meaning in the context of this project would be ill-defined (e.g., we cannot modify the sample size in response to any power calculation result and since the focus of the project is methodological any power calculation result would not be reflective of the true goals of the project).

### c. Data to be imported to Project Sandbox, if applicable

 $\boxtimes$  Program codes: SAS, SQL, Stata, R, etc.  $\boxtimes$  Code lists: NDC, ICD-9, CPT, HCPCS, etc.

If additional data is required in the sandbox, please describe below: No additional data will be imported.

### d. Data to be exported from OLDW

- $\boxtimes$  Program codes: SAS, SQL, Stata, R, etc.
- ⊠ Code lists: NDC, ICD-9, CPT, HCPCS, etc.
- Summary tables, charts and results (aggregated data)
- e. AHA data fields

Not applicable.

### 10. Contingencies, Assumptions, and Risks

We believe there are two primary sources of risk for this project:

(1) Data-related issues that may limit our ability to emulate the target trials: This is meant to include all data-related issues that independent of our project management, data management, and ability to conduct statistical analyses may lead to failure to emulate one of the target trials, e.g., because of inadequate sample size, low event rate, or extreme data missingness. We think these are low probability events. First, and most important, there are several observational studies comparing the treatments that we plan to compare in the emulation and the expanded population analyses, suggesting that there is adequate sample size to perform the planned analyses (for example, there exist numerous observational studies of rivaroxaban or liraglutide using Optum or OptumLabs data). The results reported in these studies, together with our preliminary patient count results reported in **Section 11b**, suggest that

<sup>2 Data and analytic files cannot be directly imported or exported from the virtual desktop environment without specific permissions. Exporting of individual record data from the environment is not permitted.

the proposed analyses are feasible and will have adequate sample size. Second, our use of three different cohort construction strategies (each with a different sample size and amount of information needed) makes the possibility of failure due to inadequate sample size or event rate less likely (compared to relying on a single approach). Third, conceptually, even if undesirable, emulation failures due to inadequate sample size, low event rates, or high missingness provide valuable information about our ability to use observational data to emulate target trials. For instance, it is interesting to compare the sample sizes obtained when trying to emulate the actual trials versus when trying to emulate a target trial that would have used more liberal inclusion criteria (as in the expanded population analyses). In particular, large differences in sample size (especially if they are large enough to render the trial emulation infeasible or highly imprecise) provide information about the narrowness of the actual trial's eligibility criteria and the applicability of its findings to real-world practice.

(2) Short performance period of the award: the performance period of this project is fairly short and, given the complexity of the data management and statistical analysis tasks to be performed, there is a risk of project delays. We have taken steps to mitigate such risks by budgeting sufficient programmer and analyst time. As noted in Section 7b, the PI of this proposal has previous experience with OptumLabs data in the context of a project whose aims were similar to those of the current proposal. They also have a track record of working together and are committed to the success of this project. To monitor progress the entire study team will meet weekly to discuss progress, solve problems, and set short term (~week) and medium-term goals (~month). [name] has a very close working relationship with [name] (who will be implementing methods outside the OptumLabs sandbox) and [name] (who will be working in the sandbox). Furthermore, one of our analysts ([name]) has also had hands on experience on the OptumLabs environment. And we will enlist the effort of a programmer highly experience in administrative data analyses from the many housed in the Department of Health Services Policy and Practice at Brown University. Furthermore, we believe that our team's understanding of and ability to implement the relevant causal and statistical methods is a unique strength that will allow us to make rapid progress on the analysis of the data. That said, as a last resort, to ensure we can meet project deadlines, we might omit a small number of the proposed analytical methods (e.g., use only estimating equations instead of both estimating equations and TMLE approaches to obtain doubly robust estimators, since asymptotically these two approaches are equivalent for the causal models we describe in this proposal). We do not think this is a likely contingency.

